11.3 Secondary Endpoint(s)

Overall response rate (ORR): defined as the proportion of response-evaluable participants (see [Section 12.2](#)) that achieve a best response of either CR or PR during protocol therapy.

Progression-Free Survival (PFS): defined as the duration of time from start of protocol treatment to time of disease relapse/progression, start of non-protocol anti-lymphoma therapy, or death due to any cause, whichever occurs earlier. For patients who are alive and have not had disease relapse/progression at the last follow-up, it is censored at the time of last follow-up. .

Overall Survival (OS): defined as the duration of time from start of protocol treatment to time of death due to any cause. For patients who are alive at last follow-up, it will be censored at the time of last follow-up.

Duration of Response (DOR): Defined as the time from the first achievement of PR or CR to time of PD, start of non-protocol anti-lymphoma therapy, or death, whichever earlier. Patients who never achieve PR or CR during protocol therapy are excluded. Patient who has not had any of the failure events above at last follow-up is censored at the time of last follow-up.

Toxicity: Toxicity and adverse events will be recorded using the NCI CTCAE 5.0 scale. Observed toxicities will be summarized by type (organ affected or laboratory determination such as absolute neutrophil count), severity (by NCI CTCAE v5.0 and nadir or maximum values for lab measures), date of onset, duration, reversibility, and attribution.

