5.7 Follow-Up

Following completion of protocol therapy, participants will enter follow-up.

Follow-up is comprised of:

- **Safety Follow-up**- 30 days post-last dose of protocol therapy.
 - **Note** the period for safety follow-up will be extended until stabilization or resolution for all reportable AEs (per the agreement of the Study PI) and accompanying follow-up safety report.
- **Response Follow-up**- for those who have yet to have disease progression and have not initiated a new anti-lymphoma therapy.

- **Survival Follow-up**- for all participants who have progressed OR completed Active Response Follow-Up OR initiated a new anti-lymphoma therapy. It will entail (a) Disease status (for those who have yet to progress) (b) Vital status (all participants).

Assessment time points and windows are detailed in [Section 10](#).

Note: if a participant continues therapy beyond 25 cycles with acalabrutinib for a total of 6 years of protocol therapy, the participant will only proceed with the safety follow-up visit; there will be no response/survival follow-up.

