Correlative tumor tissue ^v	X ⁿ										X ^o					
Bone marrow biopsy/ aspirate ^{p, v}	X										X					

- a. Screening activities to occur within 28 days prior to start of protocol therapy except for laboratory assessments.
- b. In the absence of treatment delay, each treatment cycle lasts 28 ± 3 days during Induction, and 28 ± 7 days during Maintenance.
- c. Maintenance phase for participants with stable disease or better response (PR or CR) at the end of Induction therapy.
- d. Activities to be performed within 72 hours prior to study drug administration.
- e. The Safety 30 days post-last dose assessments to occur 30 (± 7) days post-last dose or, if > 30 days elapsed since last dose, within 7 days after decision to end treatment. Expedited reporting will occur during this period. Safety follow-up may be extended until resolution/ stabilization of reportable AEs.
- f. For participants yet to progress, Active Follow-up will occur at 6, 12, 18 and 24 months (± 30 days for all) from last on-treatment scan until disease progression or the initiation of a new anti-lymphoma therapy.
- g. Participants who end Active Follow-up will enter Survival Follow-up. Survival assessment to occur bi-annually or as requested by the Study PI via medical record review, review of social security registry, or telephone call.
- h. *Standard physical exam* includes weight.
- i. *Vital signs*: heart rate, blood pressure, respiration rate, and temperature.
- j. *Women of childbearing potential*: Pregnancy serum test. For the screening time point, serum pregnancy test must be performed within 3 days prior to start of protocol therapy.
- k. *Screening laboratory assessments* to be performed within 14 days prior to start of protocol therapy.
- l. *Serum chemistry panel* to include: glucose, Blood Urea Nitrogen (BUN), creatinine, uric acid, total protein, albumin, magnesium, bicarbonate, calcium, inorganic phosphorous, sodium, potassium, chloride, total bilirubin, alkaline phosphatase, ALT, AST, and LDH.
- m. Correlative blood will also be collected at time of relapse. Refer to [Section 9.1.3](#) for additional information.

- n. Archival tumor tissue to be submitted post-enrollment when available. Refer to [Section 9.1.1](#).
- o. If safe and feasible, submission of left-over tissue from a standard of care tumor biopsy (fresh core or excisional biopsy) for participants who progress/relapse during study is encouraged. Refer to [Section 9.1.1](#).

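### PFS and DOR are censored at last follow-up without requiring a disease assessment at that date, so unassessed time can count as progression-free

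*Combined protocol and SAP*

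**What the plan says.** Section 11.3 censors PFS at the last follow-up ("For patients who are alive and have not had disease relapse/progression at the last follow-up, it is censored at the time of last follow-up") and DOR likewise: "Patient who has not had any of the failure events above at last follow-up is censored at the time of last follow-up". OS uses the same date. Neither 11.3 nor the analysis plan in 12.5 links the PFS or DOR date to a disease assessment, although 11.1 bases progression on the Lugano criteria, with PET-CT or CT.

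Scheduled staging off treatment is finite. Study Calendar footnote f reads "Active Follow-up will occur at 6, 12, 18 and 24 months (± 30 days for all) from last on-treatment scan". Patients who complete this without progressing pass into Survival Follow-up, for which footnote g reads "Survival assessment to occur bi-annually or as requested by the Study PI via medical record review, review of social security registry, or telephone call". Section 5.7 describes the content of that phase: "It will entail (a) Disease status (for those who have yet to progress) (b) Vital status (all participants").

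Section 17.5 also lets a patient give up treatment and every active procedure but stay in chart review and survival follow-up.

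**The concern.** A single censoring date serves endpoints that need different information. A registry entry or a call can show that a patient is alive. Neither need show that the lymphoma has not progressed. If such a contact is the last follow-up, 11.3 as written moves the PFS and DOR censoring date forward to it, and the interval since the last real evaluation counts as progression-free.

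The error runs one way: missed progressions keep patients in the risk set and hold the curve up. It falls in the tail, where durability of remission, part of the stated rationale for the regimen, would be read. Section 2.3 sets the comparison at a PFS of under 4 years for BR. For a patient who completes therapy, scheduled scans end at about that point.

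**Working it through.** **1. The plan's own figures.** The documents give no design figure for PFS or DOR. The only powered calculation is the Simon design for CR (stop at 2 or fewer of 9; promising at 10 or more of 24). An exact binomial calculation gives type I error 0.0485, power 0.8055 and early-stop probability 0.6007 at a 25% CR rate, in agreement with 12.1. None of these uses PFS or DOR.

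**2. What a follow-up contact must contain.**

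| Source | Content |
|---|---|
| 11.3 | PFS, DOR and OS all censored at last follow-up |
| 5.7 | Survival Follow-up includes disease status if not yet progressed |
| Footnote g | Record review, registry or telephone all suffice |
| 17.5 | Survival follow-up may continue after all active procedures stop |

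Section 5.7 states an intention. No section states the method, and two of the three methods in footnote g need not yield disease status.

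**3. When it applies, for a patient completing 25 cycles.**
- Therapy: 25 × 28 = 700 days; 700 / 30.4375 = 23.0 months.
- Last scheduled scan: 23.0 + 24 = 47.0 months.
- Gap under the Study Schema's 6-year maximum: 72 − 47 = 25 months.
- Gap under the synopsis participant duration of 5.5 years: 66 − 47 = 19 months.
- Gap if the calendar header of about 2 years covers all follow-up: about 0.

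A patient who stops after the C4 scan without progression (3 × 28 = 84 days, or 2.8 months) would finish Active Follow-up at about month 26.8. The 17.5 route can open a gap at any time.

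**4. Size of the bias.** Assumptions, not document figures: exponential PFS, a share q of progressions after month 47 captured, nobody stopping early, deaths not modelled separately. With λ = ln 2 / median,

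estimated S(t) = exp(−47λ) × exp(−qλ(t − 47)).

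Median 60 months (assumed), λ = 0.01155:

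| t | True (q = 1) | q = 0.5 | q = 0 |
|---|---|---|---|
| 60 months | 50.0% | 53.9% | 58.1% |
| 72 months | 43.5% | 50.3% | 58.1% |

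A simulation in which each late event has a 50% chance of being found gives 54.1% at 60 months, against 53.9% by the formula. The 72-month row can apply only to early enrollees: 7 years of study less 2 years of accrual leaves the last patients about 60 months.

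With the BR median of 35.4 months from 2.1.2.1, simulated 60-month PFS is 30.9% true, 35.3% at q = 0.5 and 39.8% at q = 0. The median stays near 35.3 months in all three cases. If 20% stop after the C4 scan without progression (assumed), the median becomes 36.3 months (q = 0.5) or 37.6 months (q = 0), against 35.2 months with last-scan censoring.

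**5. Against sampling error.** With 24 patients, a 95% interval near 50% is roughly ±1.96 × √(0.25/24) = ±20 points, before any loss from censoring. The shift is smaller than this, but it is systematic.

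**The case against.** A reader might infer that after Active Follow-up nobody looks for progression and the calendar has no scan. The documents do not support that. Section 5.7 calls for disease status in patients yet to progress. The imaging row of the calendar, in the text available for review, carries a mark that lines up with the Survival column. Its columns are not reliably aligned, so it can prove neither that a scan is scheduled nor that none is.

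The other side has further points. Record review comes first in footnote g and can reveal restaging or relapse. New anti-lymphoma therapy and death are PFS and DOR events, so a treated or fatal relapse counts once recorded. Read with 5.7, the last follow-up could mean one at which disease status was obtained. The 25-month gap is the upper end. Patients who continue acalabrutinib are imaged every 6 months, and those who reach 6 years of therapy have no response or survival follow-up. The endpoints are secondary and untested.

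All this limits the size and likelihood of the bias. It does not remove the defect: the favourable reading has to be supplied by the reader, because 11.3 does not say it and footnote g permits contacts that would not satisfy it.

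A simple switch to last-scan censoring also has a flaw. If event-free patients leave the risk set at their last scan while later deaths, new therapies and chart-reported progressions still count, those events fall on a depleted risk set and push the curve down.

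**Conclusion.** The concern holds in limited form. As written, 11.3 can count unassessed time as progression-free and bias the PFS and DOR tail upward. For patients completing therapy the effect lies mainly after about month 47, over a gap of about 0 to 25 months. It can reach earlier times, and the median, through patients who stop early without progression or give up active procedures under 17.5.

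Under the assumed exponential PFS with a 60-month median, true 60-month PFS of 50.0% would be estimated between 50.0% (all late progressions captured) and 58.1% (none captured, a worst case). The true captured share cannot be known from the documents. The change is worth making because it is cheap and the possible bias has one direction. OS is unaffected, as are the CR analysis, sample size and stopping rules.

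**What to change.** - **Section 11.3:** censor PFS and DOR at the last documented evaluation of disease status adequate to exclude progression. This may be a scan, or source-documented restaging or clinical disease evaluation, including one found on record review. Registry or telephone contacts that give vital status only extend OS alone.
- **Section 12.5:** add a sensitivity analysis that also censors, at that same date, events first found long after the last evaluation. Set the interval that counts as long in advance; the 6-month scan spacing is a natural unit.
- **Section 5.7, footnote g and the calendar imaging row:** reconcile them on how disease status is obtained in Survival Follow-up. State which duration governs: the header's 2 years, 5.5 years or 6 years.

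The cost is a few sentences, one extra analysis, and recording the date and basis of each disease-status entry if the follow-up form does not already hold them. No visits are added. Reported PFS and DOR follow-up will be somewhat shorter. If every follow-up already includes an adequate evaluation, the primary estimates will not change.

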11.4 Exploratory Endpoint(s)

Exploratory endpoints include T-cell population and function measures, gene expression/mutation profiles, and MRD assessed by ClonoSeq assay.

12.0 STATISTICAL CONSIDERATIONS

12.1 Study Design

This is a multicenter, single-arm Phase 2 study evaluating AU2 therapy for patients with previously untreated MCL. Patients will first receive 6 cycles of AU2 (acalabrutinib + umbralisib + ublituximab) induction; those who achieve SD or better response after induction will then receive 19 cycles of maintenance with the 3 agents, during which ublituximab will only be given every 2 cycles. Each cycle will be 28 days. Participants may continue therapy with acalabrutinib beyond 25 cycles of Induction + Maintenance therapy at the treating physician's discretion. Response will be evaluated just prior to C4, C7 (End of Induction), C14, C20 , EOM (end of maintenance), every 6 months thereafter until end of protocol therapy (if patient continues with oral agents only beyond 25 cycles), and at Safety visit.

The primary endpoint is complete response (CR) rate after AU2 induction therapy. Secondary endpoints include toxicities of AU2 induction and maintenance therapy, overall response rate to protocol therapy, duration of response, progression free survival, and overall survival.

The study sample size is based on the desire to discriminate a promising CR rate of 50% (alternative hypothesis) from a disappointing CR rate of 25% (null hypothesis) after AU2 induction. These response rates were chosen because 1) BR, a current standard, has been associated with an ORR of 80-90% and a CR rate of 40% [5, 7]; 2) In the phase 2 ACE-LY-004 trial in R/R MCL, treatment with acalabrutinib was associated with an ORR of 81% and a CR rate of 40% [39]. However, it is anticipated that this study will enroll a higher proportion of patients with high-risk MCL (*TP53* aberrations, CK) where BR is ineffective.

Simon's optimal two-stage design will be used. In the first stage, 9 evaluable patients will be accrued. If there are 2 or fewer CRs in these 9 patients, the study will be stopped. Otherwise, 15 additional evaluable patients will be accrued for a total of 24. The null hypothesis will be rejected and AU2 induction therapy will be considered promising if 10 or more CRs are observed in 24 evaluable patients. This design yields a 1-sided type I error rate of 0.05 and power of 0.8. When the CR rate is disappointing (25%), there is an 60% chance that the study will be terminated after the first stage.

12.2 Evaluable Participants and Participant Replacement

- ***Evaluable for toxicity:*** Patients who receive at least one dose of protocol therapy are evaluable for toxicity.
- ***Evaluable for response endpoints:***

Evaluable patients are defined as eligible participants who have received at least one cycle of Induction therapy and have at least one disease evaluation post-baseline.

Patients will be evaluable and be considered non-CR in the primary 2-stage response evaluation, if the reason why they did not finish at least 1 cycle of induction therapy or discontinued induction therapy prior to having a response assessment was progressive disease or toxicity. All other patients without 1+ cycle or 1+ response assessment post-baseline, such as those who terminated due to patient refusal or investigator decision, will be inevaluable and replaced.

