5.6 Duration of Therapy and Criteria for Removal from Protocol Therapy

Participants will receive protocol therapy until one of the below criteria are met:

- Confirmed Disease progression per 2014 Lugano classification
- Completed protocol therapy
- Participant is deemed intolerant to protocol therapy because of toxicity, despite dose modification/delay
 - **Note:** If one agent is discontinued due to toxicity, then the participant may continue to receive the other study agents
- General or specific changes in the patient's condition which render the patient unacceptable for further treatment in the judgment of the investigator
- Withdrawal of consent for further protocol therapy (See [Section 17.5](#))

Once participants meet criteria for removal from protocol therapy, the participant should then proceed to follow-up assessments ([Section 5.7](#)).

Documentation of the reason for discontinuing protocol therapy and the date effective should be made in the Electronic Health Record/medical record and appropriate eCRF.

The COH DCC and the Study PI should be promptly notified of the change in participant status.

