5.8 Duration of Study Participation

Study participation may conclude when any of the following occur:

- Completion of study activities (treatment and follow-up)
- Withdrawal of consent (See [Section 17.5](#))
- Patient decided to proceed with autologous transplantation
- Participant is lost to follow-up. All attempts to contact the participant must be documented.
- At the discretion of the investigator for safety, behavioral, study termination or administrative reasons

Documentation of the reason for discontinuing study participation and the date effective should be made in the Electronic Health Record/medical record and appropriate eCRF.

The COH DCC and the Study PI should be promptly notified of the change in participant status.

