12.3 Sample Size and Accrual Rate

The 2-stage Simon optimal design, as described above, will require up to 24 response evaluable patients. Accounting for up to 10% inevaluable patients that need to be replaced, the maximum accrual for the study will be 27 patients. Combining all participating sites, we project that the study accrual can be completed within 2 years, with an estimated accrual rate of approximately 1 patient per month.

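### Section 12.2 replaces early leavers unless they stopped for progression or toxicity, and no CR rate in all treated patients is planned, so the exclusion can only raise the observed CR rate

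*Combined protocol and SAP*

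**What the plan says.** To be evaluable for response under Section 12.2, an eligible patient needs at least one induction cycle and at least one post-baseline disease evaluation. A patient who misses either one stays in the two-stage evaluation as a non-CR if the cause was progressive disease or toxicity. All others, "such as those who terminated due to patient refusal or investigator decision, will be inevaluable and replaced".

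Section 11.2 defines the CR rate, and Section 11.3 the ORR, on this response-evaluable set. Section 12.5 repeats that denominator and lists no analysis of all treated patients. The toxicity set in Section 12.2, by contrast, is everyone with at least one dose.

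On timing, Section 12.1 states: "Response will be evaluated just prior to C4, C7 (End of Induction"; it also plans a response evaluation at the Safety visit. Among the grounds for ending therapy, Section 5.6 lists, separately from progression and toxicity, "General or specific changes in the patient's condition which render the patient unacceptable for further treatment in the judgment of the investigator".

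On size, Section 12.1 sets out to "discriminate a promising CR rate of 50% (alternative hypothesis) from a disappointing CR rate of 25% (null hypothesis"), and Section 12.3 adds: "Accounting for up to 10% inevaluable patients that need to be replaced, the maximum accrual for the study will be 27 patients".

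**The concern.** Refusal and investigator decision are named as reasons for replacement. Death from another cause and clinical decline are not named, but they fall into the residual group when they are not recorded as progression or toxicity. A patient taken off under the Section 5.6 ground quoted above, without a confirming scan, can be coded as an investigator decision and so leave the denominator.

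These patients have no recorded CR. Leaving them out instead of counting them as non-CR moves the observed rate in one direction only, at stage 1, at the final decision and in the only planned estimate. A single-arm trial has no control group in which the same exclusion would offset this. Inclusion can also turn on whether a scan was obtained: of two patients who complete one cycle and stop for the same reason, the one scanned at the Safety visit counts and the other is replaced.

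**Working it through.** **Inputs.** Null CR rate 0.25, alternative 0.50, n1 = 9, stop at 2 or fewer CRs, n = 24, success at 10 or more (Section 12.1). Up to 10% inevaluable, maximum accrual 27 (Section 12.3), hence at most 27 − 24 = 3 replacements if 24 evaluable patients are to be reached. Cycle length 28 days (Section 12.1). The number of dosed patients actually replaced is not given; it is treated as an assumption over the range 0 to 3.

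**Step 1: the plan's own figures.** With X1 ~ Bin(9, p) and X2 ~ Bin(15, p):

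- Early stop = P(X1 ≤ 2). At p = 0.25: 0.0751 + 0.2253 + 0.3003 = 0.6007.
- P(promising) = Σ over x = 3 to 9 of P(X1 = x) · P(X2 ≥ 10 − x). At p = 0.25 this is 0.0485; at p = 0.50 it is 0.8055.

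These agree with the stated 60%, 0.05 and 0.8. The design arithmetic is correct.

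**Step 2: who can be replaced.** The first scheduled on-treatment scan comes after 3 × 28 = 84 days, or 12 weeks. The Safety visit (Section 10, footnote e: 30 ± 7 days after the last dose, or within 7 days of the decision to stop if more than 30 days have already passed) should make most patients with one full cycle evaluable sooner. That leaves mainly (i) stops before one full cycle for a reason other than progression or toxicity, (ii) deaths before any scan that are attributed to neither, and (iii) patients who miss the Safety-visit evaluation.

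**Step 3: illustration.** Assume that the CR rate in all treated patients is exactly 25% and that m replaced patients were dosed and had no CR. The rate in the evaluable set is then 0.25 × (24 + m)/24. Applying the Step 1 formulas:

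| Replaced / treated | Evaluable-set rate | Early stop | P(promising) | 10 CRs among all treated |
|---|---|---|---|---|
| 0 / 24 | 25.0% | 0.601 | 0.0485 | 41.7% |
| 1 / 25 | 26.0% | 0.572 | 0.062 | 40.0% |
| 2 / 26 | 27.1% | 0.543 | 0.078 | 38.5% |
| 3 / 27 | 28.1% | 0.514 | 0.097 | 37.0% |

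The last row is 3/27 = 11.1%, slightly above the 10% in Section 12.3. At exactly 10% the evaluable-set rate is 0.25/0.90 = 27.8% and P(promising) is 0.090.

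**Step 4: what counting them as non-CR would cost.** If 50% holds only among patients who reach a scan, and a share d of the 24 are early leavers counted as non-CR, the overall rate is 0.50 × (1 − d). Power is then 0.737 at d = 5% (rate 47.5%) and 0.656 at d = 10% (rate 45.0%). If 50% already means all treated patients, power stays at 0.805.

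**The case against.** The strongest reply is that the plan defines its target in evaluable patients. Section 11.2 says so, and Section 12.1 counts both stages, 9 and then 24, in the same terms. For that target the type I error is 0.0485 and nothing is inflated. This stands. The figures in Step 3 apply only if 25% is read as a rate in all treated patients, and the documents do not say that it is.

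Second, the two reasons most clearly tied to treatment failure, progression and toxicity, are already counted as non-CR. Early deaths also remain events for PFS and OS (Section 11.3). Both are true. Neither supplies a CR rate or ORR in all treated patients.

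Third, the 3 spare places are an accrual allowance, not a forecast of dosed dropouts. They may be used by ineligible patients or by registered patients who never start (Section 4.3). This also stands, so the size is a range and not an estimate.

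A reader might infer two stronger things that the documents do not support:

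- *That any patient who leaves in the first 12 weeks is replaced.* The Safety-visit evaluation makes most patients with one full cycle evaluable, so the group is narrower.
- *That everyone removed is a likely non-responder, including those who leave for transplant.* Section 5.8 lists "Patient decided to proceed with autologous transplantation" only as a reason for ending participation and says nothing about response. Some patients who refuse might have responded. What is known is that none has a documented CR.

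**Conclusion.** The point holds as a limited weakness in the analysis population, not as an error in the design. The direction is certain: compared with counting them as non-CR, removing patients without a documented CR can only raise the observed rate. The size is not known. It is zero if no dosed patient is replaced. At the accrual maximum, the smallest successful result of 10/24 (41.7%) would be 10/27 (37.0%), and the chance of a false positive would be 0.097. That upper figure needs three assumptions together: 25% is the rate in all treated patients, all 3 replaced patients were dosed, and none would have had a CR. A reader might conclude that the trial's stated type I error is wrong; it is not, for the population in which the plan states it. What is missing is a result for everyone treated, and a rule that keeps outcome-related early exits in the denominator.

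**What to change.** 1. **Section 12.5:** report the CR rate and ORR, each with an exact 95% confidence interval, in all eligible patients who received at least one dose, counting a missing assessment as non-response, beside the response-evaluable figures. This needs no new data and no extra patients. The rate shown may be slightly less favourable.
2. **Section 12.2:** count as an evaluable non-CR any eligible dosed patient with no post-baseline assessment because of death from any cause, an investigator decision for clinical deterioration, or the start of other anti-lymphoma therapy. Keep replacement for patients never dosed and for stops unrelated to the disease or its treatment. Refusals unrelated to either would still be replaced, so this removes only part of the effect; item 1 shows the rest.
3. **Section 12.1:** state whether the 25% and 50% rates describe all treated patients or only those who reach an assessment. If the latter, item 2 lowers power as in Step 4, and the sponsor should accept that knowingly.

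If only one change is made, item 1 is the one to make: it costs a table line and leaves the decision rule untouched.
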